### **11.1.2 Evaluation of Best Overall Response**

The best overall response is the best response observed until progression/recurrence and is determined as indicated in the table below:

Target Lesions	Non-Target Lesions	Evaluation of New Lesions	Best Overall Response
CR	CR	No	CR
CR	SD	No	PR
PR	Non-PD	No	PR
SD	Non-PD	No	SD
PD	Any	Yes or No	PD
Any	PD	Yes or No	PD
Any	Any	Yes	PD

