#### **11.1.1 irRECIST**

Measurable disease/non-measurable and target/non-target criteria- using one-dimensional measurements (simulating RECIST 1.1):

The following definitions and criteria (irRECIST) should be used for the baseline evaluations of existing disease, and for the ongoing evaluation of tumor measurements according to Nishino, an adaptation of Wolchok (22).

**Measurable lesions** - lesions that can be accurately measured in at least one dimension with longest diameter (LD)  $\geq$  10 mm using CT, MRI, or caliper measurements or  $\geq$ 20 mm with x-

ray. Lymph nodes which are defined as measurable at baseline must meet the criterion of a short axis  $> 15\text{mm}$  by CT scan.

**Non-measurable lesions** - all other lesions including small lesions (LD  $< 10\text{ mm}$  with CT, MRI, or caliper measurements or  $<20\text{ mm}$  with x-ray).

**Target Lesions** - all measurable lesions, up to a maximum of **five lesions**, should be identified as *target* lesions to be measured and recorded on the medical record at Screening. The *target* lesions should be representative of all involved organs. In addition, *target* lesions should be selected based on their size (lesions with the longest diameters), their suitability for accurate repeat assessment by imaging techniques, and how representative they are of the patient's tumor burden. At screening, a sum of the products of diameters (SPD) for all *target* lesions will be calculated and considered the baseline sum of the products of diameters. Response criteria to be followed are listed below. The baseline sum will be used as the reference point to determine the objective tumor response of the *target* lesions at tumor assessment (TA).

**Non-Target Lesions** - measurable lesions, other than *target* lesions, and all sites of non-measurable disease, will be identified as *non-target* lesions. *Non-target* lesions will be recorded on the medical record and should be evaluated at the same assessment time points as the *target* lesions. In subsequent assessments, *non-target* lesions will be recorded as "stable or decreased disease," "absent," or "progression."

**New Lesions and non-target lesions** - In irRECIST a new lesion does not automatically indicate progressive disease

New measurable lesions are added to the sum of the longest diameters of the previously existing target lesions, and the sum of the longest diameters is followed at each subsequent tumor assessment

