New measurable lesions are defined using the same criteria as for baseline target lesions in RECIST 1.1. New measurable lesions shall be prioritized according to size and the largest lesions shall be selected as new measured lesion up to 2 lesions per organ and 5 new lesions total.

Non-target lesions (baseline and new non measurable) are used for determination of Complete Response. The RECIST 1.1 definitions for the assessment of non-target lesions apply.

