### **Response Categories:**

- **Complete Response (irCR):** disappearance of all not-nodal target lesions and non-target lesions in two consecutive observations not less than 4 weeks apart. In addition, any pathological lymph nodes assigned as target lesions must have a reduction in short axis to  $<10\text{mm}$  (sum of diameters may be greater than zero at the time of CR, if nodal lesion are including as target lesions).
- **Partial Response (irPR):** at least a 30% decrease in the sum of diameters of all target lesions including new target lesion in two consecutive observations not less than 4 weeks apart, taking as reference the baseline sum of diameters.

- **Progressive Disease (irPD):** at least a 20% increase in the sum of diameters of all measured target lesions including new measurable lesions. The reference for irPD will be the smallest sum of diameter of all target lesions recorded at original baseline or subsequent. Progression must be confirmed with a follow up scan no less than 4 weeks and no more than 8 weeks after the first scan that shows disease progression.
- **Stable Disease (irSD):** neither a sufficient shrinkage to qualify of irPR or irCR, or an increase in the sum of target lesions which would qualify for irPD.

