### **11.3 Stopping Rules**

Up to a total of 34 response evaluable patients are required. Generally, evaluable patients should have baseline scans and one 6 week follow-up scan to be evaluable for response assessment. Patients should also have received at least 2 cycles of Pembrolizumab to be considered evaluable for response. Enrollment and evaluation of response based on irRECIST.

An initial analysis will be done on the first 13 response evaluable patients enrolled to the Pembrolizumab treatment regimen. Recruitment will be terminated (stopped) if there are only 0 – 1 responses (irCR/irPR). If there are 2+ responses in 13 evaluable patients, recruitment will be expanded with this treatment regimen to up to an additional 21 evaluable patients.

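### The best-overall-response table in 11.1.2 scores any new lesion as PD while 11.1.1 adds new lesions to the sum, so it is ambiguous who counts as a responder

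*Combined protocol and SAP*

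**What the plan says.** Section 11.1.1 sets the irRECIST rules. On new lesions it states: "In irRECIST a new lesion does not automatically indicate progressive disease". It continues: "New measurable lesions are added to the sum of the longest diameters of the previously existing target lesions". Under Response Categories, irPR is "at least a 30% decrease in the sum of diameters of all target lesions including new target lesion", required "in two consecutive observations not less than 4 weeks apart, taking as reference the baseline sum of diameters". irPD is a rise of at least 20% in the total that includes new measurable lesions, measured from the smallest sum, with no separate trigger for a new lesion. irSD is what lies between. On lesions too small to measure, 11.1.1 says: "Non-target lesions (baseline and new non measurable) are used for determination of Complete Response".

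Section 11.1.2 then states: "The best overall response is the best response observed until progression/recurrence and is determined as indicated in the table below". In its table every row that ends in CR, PR or SD requires *No* under new lesions, and the last row gives PD for any target status and any non-target status once a new lesion is present.

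The primary objective (1.1) is the rate of irPR plus irCR by irRECIST. Section 11.3 says "Enrollment and evaluation of response based on irRECIST" and stops recruitment at 0 or 1 responses in 13. Section 12 counts irCR plus irPR and rejects the null hypothesis at 6 or more in 34.

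**The concern.** The two subsections give different answers for the same scans, and no sentence says which one governs. Whether a patient counts as a responder is the only input to the primary endpoint and to both decisions of the two-stage design, so a single patient on a cut-off can close the trial or reverse its conclusion. The clinical benefit rate is exposed in the same way, through irSD versus PD. The trial is open label with one arm, so settling the rule after scans have been read would be a choice about the primary result made with the data in view.

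**Working it through.** **1. One patient under both rules.** These measurements are illustrative and do not come from the documents. The baseline sum is 100 mm. The follow-up readings are already present at the first post-baseline scan and are the same at a second scan at least 4 weeks later.

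| Targets | New lesion | Total | Change | 11.1.1 | 11.1.2 table |
|---|---|---|---|---|---|
| 55 mm | 10 mm | 65 mm | (65 − 100)/100 = −35% | irPR, confirmed | PD |
| 90 mm | 10 mm | 100 mm | 0% | irSD | PD |

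Looking back to the best response before progression does not rescue the first patient, because no earlier follow-up scan is free of the new lesion. That is why the conflict is certain when the new lesion is there at the first scan with a total fall of at least 30%. If the lesion first appears at the confirming scan, the conflict arises only when the two-scan rule of 11.1.1 is also applied to the table.

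**2. The plan's design, reproduced.** Inputs from section 12: null 10%, alternative 25%, alpha 0.10, beta 0.20, continue at 2 or more of 13, reject at 6 or more of 34. With X1 the stage-1 responses:

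P(reject | p) = Σ over x = 2..13 of P(Bin(13, p) = x) × P(Bin(21, p) ≥ 6 − x).

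- p = 0.10: 0.0957, within alpha 0.10.
- p = 0.25: 0.8108, above 0.80.
- Chance of stopping at stage 1: 0.621 at 10% and 0.127 at 25%.
- Expected size under the null: 13 + (1 − 0.6213) × 21 = 20.95. A full search returns this same design as the one with the smallest expected size.

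The design is therefore right for whatever response definition is chosen.

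**3. Size without any assumption.** One reclassified responder moves the ORR by 1/34 = 2.9 points, and can turn 2/13 into 1/13 (stop) or 6/34 into 5/34 (not rejected).

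**4. Size under an assumed share.** Let s be the share of 11.1.1 responders who would be PD under the table. The documents give no value for s. Assume that 25% is the true rate under 11.1.1 and that patients are affected independently. The counted rate is then 0.25 × (1 − s).

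The last column is the chance that the 11.1.1 count sits on a cut-off and at least one counted responder is reclassified. With q = 1 − s:

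P(X1 = 2) × (1 − q²) + P(X1 ≥ 3, total = 6) × (1 − q⁶) + P(X1 = 2, total = 6) × q² × (1 − q⁴),

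where the three probabilities at p = 0.25 are 0.2059, 0.0433 and 0.0362. The third term covers a stage 1 that passes intact and a stage-2 responder who is lost. For s = 0.10: 0.0391 + 0.0203 + 0.0101 = 0.0695.

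| s | Counted rate | Power | Loss of power | On a cut-off and reclassified |
|---|---|---|---|---|
| 0 | 0.2500 | 0.811 | – | – |
| 2% | 0.2450 | 0.796 | 0.015 | 0.016 |
| 5% | 0.2375 | 0.771 | 0.040 | 0.038 |
| 10% | 0.2250 | 0.725 | 0.086 | 0.070 |
| 20% | 0.2000 | 0.614 | 0.197 | 0.120 |

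The chance of stopping at stage 1 rises from 12.7% at s = 0 to 17.4% at 10% and 23.4% at 20%.

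**The case against.** The strongest reply is that irRECIST already governs. The primary objective, the stopping rule and the final test all use the ir-labels, and those labels are defined only in 11.1.1. Best overall response is not invoked by any objective, stopping rule or analysis sentence. This stands as evidence of intent, and it limits the point to an ambiguity. It does not remove the conflict: 11.1.2 states without qualification that its table determines best response, it sits in the same efficacy section, and a site that applies it is following the protocol.

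Three stronger readings are tempting, and the documents do not support them.

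- A reader might infer that the primary endpoint will be mis-scored or that the trial is underpowered. The power figures rest on an assumed share, and the texts that count responses point towards 11.1.1.
- A reader might infer that the table lets an unconfirmed PR count, because it does not mention confirmation. Nothing in 11.1.2 sets aside the confirmation rule stated just before it.
- A reader might extend the point to PFS. Section 11.1.3 assesses progression by irRECIST and does not draw on best overall response, so that is not claimed.

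**Conclusion.** The conflict is in the text and needs no assumption: for a patient with a new lesion, 11.1.1 can give irPR or irSD where 11.1.2 gives PD, and no precedence is stated. The consequence is that the responder count is ambiguous for the ORR, for the stage-1 decision (1 versus 2 of 13) and for the final decision (5 versus 6 of 34), and that irSD versus PD is ambiguous for the clinical benefit rate. Its effect on this trial cannot be sized from the documents. The range above, from 0.796 down to 0.614 in power, is hypothetical and runs in one direction only because it models lost responders alone. The point should be fixed because one patient can decide either count and the correction is small.

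**What to change.** Amend the 11.1.2 table to follow 11.1.1 before the stage-1 or final count is relied on:

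- (a) Base the first column on the sum of target plus new measurable lesions.
- (b) Delete the last row (any new lesion = PD) and the no-new-lesion condition in the rows that end in PR or SD. Keep that condition in the CR row.
- (c) Use the irCR, irPR, irSD and irPD labels of 11.1.1, with their confirmation rules.
- (d) Give every combination an explicit category. Target CR with non-target CR and a new non-measurable lesion needs one. It is not irCR, in line with 11.1.1, but otherwise would match no row. State also whether such a lesion can enter the non-target PD row that is kept, since 11.1.1 does not settle this.

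As separate housekeeping, the Target Lesions paragraph of 11.1.1 computes a figure at screening that "will be calculated and considered the baseline sum of the products of diameters", while irPR is taken against a sum of diameters. Align the first with the second.

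The cost is one amendment with IRB approval (16.11), covering one table and one baseline sentence. Patients already classified should be rescored from existing scans, and any who lack the confirming scan that irPR needs should be noted. Sample size and cut-offs do not change.

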## SCHEMA

## 1 OBJECTIVES

### 1.1 Primary Objectives and Endpoint

To evaluate overall response rate of pembrolizumab (irPR + irCR) using immune related (ir)RECIST in patients with non-pulmonary, high grade neuroendocrine carcinoma.

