## **12 STATISTICAL CONSIDERATIONS**

A Simon Optimum Two-Stage design will be used with a Type I error rate alpha equal to 0.10 and a Type II error rate beta equal to 0.20. The null hypothesis is an objective response rate (irCR + irPR) of 10% or lower. The alternative hypothesis is an objective response rate of 25% or higher. With these design parameters, the first stage will consist of 13 patients. If there are 2 or more responses in 13 patients, up to an additional 21 evaluable patients will be recruited for a maximum sample size of 34 evaluable patients. If there are 6 or more responses in up to 34 evaluable patients the null hypothesis will be rejected. If there are 5 or fewer responses 34 evaluable patients the null hypothesis will not be rejected. It is estimated that it may be necessary to enroll up to 40 patients to accrue 34 response evaluable patients.

Kaplan-Meier methods and associated confidence intervals will be used to analyze PFS and OS. All subjects assessed for progression will contribute to this analysis. The clinical benefit rates (irCR + irPR + irSD) will be analyzed by tabulating the observed counts and proportions together with exact binomial confidence intervals.

Tumor tissue will be analyzed for the correlation of biomarkers to response rate.

- 1) Tissues analyzed for correlation of tumor mutational burden will be categorized as high, medium and low burden.
- 2) Tissues analyzed for correlation of PD-L1 expression will be categorized as high or low.
- 3) Tissues analyzed for correlation to proliferative index will be categorized as Ki-67 20-55% or Ki-67 > 55%.

Fisher's exact test will be used to analyze each of these biomarkers. Two sided p-values < 0.05 will be regarded as statistically significant.

Safety will be analyzed by tabulating adverse events.

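### Section 11.1.2 does not carry over the confirmation required in 11.1.1, and its new-lesion row contradicts 11.1.1, so patients near the 2-of-13 and 6-of-34 cut-offs could be misclassified

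*Combined protocol and SAP*

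**What the plan says.** - **Primary endpoint (section 1.1):** "overall response rate of pembrolizumab (irPR + irCR) using immune related (ir)RECIST". Section 11.3 (the 13-patient look) and section 12 (the hypotheses) count the same two categories. Section 12 puts it as "The null hypothesis is an objective response rate (irCR + irPR) of 10% or lower".
- **Response (section 11.1.1, Response Categories):** irPR needs the required shrinkage "in two consecutive observations not less than 4 weeks apart, taking as reference the baseline sum of diameters". irCR carries the same repeat requirement.
- **Progression (same place):** "Progression must be confirmed with a follow up scan no less than 4 weeks and no more than 8 weeks after the first scan" on which it appears.
- **New lesions (section 11.1.1):** a new lesion is not by itself progression. New measurable lesions are added to the sum of diameters, and the percentage rules apply to that total.
- **Best overall response (section 11.1.2):** "The best overall response is the best response observed until progression/recurrence and is determined as indicated in the table below". The table combines target, non-target and new-lesion findings under the labels CR, PR, SD and PD, without the ir prefix. It has no confirmation column or footnote. Its last row gives PD whenever there is a new lesion, whatever the other findings.
- **Evaluability (sections 11.1 and 11.3):** baseline scans, one 6-week scan and at least 2 cycles are enough.

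The protocol does not say which of 11.1.1 and 11.1.2 governs where they differ.

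**The concern.** Section 11.1.2 is the only place where lesion-level findings are combined into one result per patient, so an assessor is likely to work from it. It reads as a conventional RECIST table placed after immune-related definitions, and it leaves two questions open and one in conflict:

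1. Does PR in the table mean irPR, which has to be confirmed, or the finding at one scan?
2. Does the period up to progression end at the first scan showing it, or at the confirmed event?
3. Is a new lesion PD (11.1.2), or an addition to the sum (11.1.1)?

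The answers can move the primary count either way. Counting single-scan responses raises it. Closing the window at an unconfirmed PD, or at any new lesion, removes the late responders that immune-related criteria are meant to keep. The cut-offs leave little room: 2 against 1 response in 13, and 6 against 5 in 34 (6/34 = 17.6%, 5/34 = 14.7%). One patient classified differently can change either decision.

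**Working it through.** **Step 1. Three patients under each section.** Scans are every 6 weeks through week 36 (section 9, calendar footnote 10). A scan 6 weeks after a first PD therefore falls within the 4 to 8 week confirmation window. Section 7.8 requires progression to be confirmed before a patient is discontinued for it, so patient (b) can reach the later scans.

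| Patient | Under 11.1.1 | Under 11.1.2 read literally |
|---|---|---|
| (a) Target lesions only: 35% fall at week 6, then confirmed growth | Not irPR (no second observation) | PR |
| (b) Target lesions only: 25% rise at week 6, not confirmed; 35% falls at weeks 12 and 18 | irPR (two scans 6 weeks apart) | PD at week 6; window may close |
| (c) New measurable lesion, but the sum including it is at least 30% below baseline at two scans 6 weeks apart | irPR | PD (last row) |

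Patients (a) and (b) depend on how 11.1.2 is read. Patient (c) does not: the two sections give different answers.

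A patient with only the 6-week scan is evaluable but cannot have shown a confirmed response. Section 11.1.2 does not say how to score that patient.

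**Step 2. Reproduce the design.** Inputs from section 12: null rate 0.10, alternative 0.25, "Type I error rate alpha equal to 0.10" and "Type II error rate beta equal to 0.20". Stage 1 has 13 patients and continues with 2 or more responses. Stage 2 adds 21, and the null is rejected with 6 or more of 34. With b(x; n, p) the binomial probability, the chance of rejecting is

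R(p) = sum over x = 2 to 13 of b(x; 13, p) × P[Bin(21, p) ≥ 6 − x].

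- Early stopping at 10%: 0.9^13 + 13 × 0.1 × 0.9^12 = 0.254 + 0.367 = 0.621.
- Expected sample size at 10%: 13 + (1 − 0.621) × 21 = 21.0.
- R(0.10) = 0.0957, within 0.10.
- R(0.25) = 0.8108, above 0.80.

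A grid search for the smallest expected sample size under the null, subject to both error limits, returns 13/1 and 34/5. The stated design reproduces.

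**Step 3. Sensitivity to misclassification.** Take 10% and 25% as confirmed rates and shift the rate that is actually counted. The shifts are assumptions; the documents give no rate for unconfirmed PR or for response after unconfirmed PD.

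| Assumed shift (points) | Chance of declaring activity, confirmed rate 10%, single-scan PRs added | Power, true rate 25%, responders lost after unconfirmed PD |
|---|---|---|
| 0 | 0.096 | 0.811 |
| 1 | 0.134 | 0.779 |
| 2 | 0.178 | 0.744 |
| 3 | 0.228 | 0.705 |
| 5 | 0.338 | 0.614 |

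Each column moves one mechanism alone. The two act in opposite directions, and their net effect is unknown.

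**The case against.** A reader might infer that the plan drops confirmation, so that a single-scan PR is a response by rule. The documents do not support that. Section 11.1.1 defines irCR and irPR only as repeated findings, so there is no unconfirmed irPR category. Sections 1.1, 11.3 and 12 count irCR and irPR, and neither 11.3 nor 12 mentions best overall response. Section 11.1.2 neither repeats the confirmation nor waives it. On the ordinary reading, patient (a) is not a responder.

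Similarly, a reader might infer that an unconfirmed PD ends the response window. Sections 4.4, 7.8, 9 and 11.1.1 all ask for progression to be confirmed, and 11.1.3 says it is assessed by irRECIST.

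These arguments settle the likely intent, but they do not close the gap. The table already departs from 11.1.1 on new lesions, so it cannot be assumed to keep the confirmation silently. Section 11.1.1 itself describes the first, unconfirmed scan as showing progression, so the unqualified word in 11.1.2 can fairly be taken to mean that scan. No other rule combines the three lesion types into one result per patient.

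The objection that the size is assumed stands in full: the table in Step 3 shows how sensitive the rule is, not what will happen.

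**Conclusion.** The point holds as an unresolved gap between 11.1.1 and 11.1.2, together with one direct contradiction on new lesions. It affects classification for the primary ORR and for the 13-patient look. Confirmed irCR and irPR is the better reading of sections 1.1, 11.1.1, 11.3 and 12, so it would be wrong to say that the protocol counts single-scan responses.

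No design figure is in error: 13/1 and 34/5 meet both error limits. The size of the effect cannot be derived from the documents. If 10% and 25% are confirmed rates, a 1-point shift in the counted rate is enough to cross either limit (0.134 against 0.10; 0.779 against 0.80). That is reason to settle the rule before borderline patients are classified. The change should be made; it alters neither the sample size nor the cut-offs.

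**What to change.** In section 11.1.2:

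- State that best overall response uses irCR and irPR confirmed per 11.1.1, and that a response seen on one scan only is not counted as irCR or irPR for the ORR. Say how it is scored instead.
- State that the response window ends at confirmed irPD, so an unconfirmed rise does not close it. Say how a first PD that never gets a confirming scan (for example after death or withdrawal) is scored.
- Relabel the table irCR, irPR, irSD and irPD, and at the same time reconcile its new-lesion entries with 11.1.1. Relabelling alone would make every new lesion irPD and entrench the contradiction.
- Reconcile the confirmation interval for progression, which is 4 to 6 weeks in section 4.4 but 4 to 8 weeks in sections 7.8, 9 and 11.1.1, so that confirmed irPD has one meaning.

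The cost is a few sentences and new table labels. The reported ORR may be slightly lower than under a single-scan count. The secondary clinical benefit rate (irCR + irPR + irSD) will depend on how single-scan responses are scored: as irSD they stay in it, otherwise they may drop out.
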